2 LIST OF ABBREVIATIONS

AE	Adverse Event
AED	Anti-epileptic Drug
ANC	Absolute Neutrophil Count
AST	Aspartate Aminotransferase
BCS	Brain Subscale
BDI	Beck Depression Inventory
CBC	Complete Blood Count
CMP	Comprehensive Metabolic Panel
CNS	Central Nervous System
CPC	Cancer Protocol Committee
CTCAE	Common Terminology Criteria for Adverse Events
DCI	Duke Cancer Institute
DOCR	Duke Office of Clinical Research
DSMB	Data and Safety Monitoring Board
DUHS	Duke University Health System
DUMC	Duke University Medical Center
FACT-Br	Functional Assessment of Cancer Therapy-Brain
FACT-Cog	Functional Assessment of Cancer Therapy-Cognition
FACIT-F	Functional Assessment of Cancer Therapy-Fatigue
FDA	Food and Drug Administration
H&P	History & Physical Exam
HRPP	Human Research Protections Program
IRB	Institutional Review Board
KPS	Karnofsky Performance Status
NCI	National Cancer Institute
p.o.	per os/by mouth/orally
PRO	Patient-Reported Outcome
PRTBTC	Preston Robert Tisch Brain Tumor Center
QoL	Quality of Life
SAE	Serious Adverse Event
TEAE	Treatment-Emergent Adverse Events

3 PROTOCOL SYNOPSIS AND RESEARCH SUMMARY

3.1 Purpose

This is a Phase 4 single-arm study assessing the efficacy of perampanel as an adjunctive anti-epileptic drug (AED) in patients with primary glioma presenting refractory partial onset seizure activity.

Primary Objective:

1. To determine the efficacy of perampanel as an adjunctive AED in patients with primary glioma presenting refractory partial onset seizure activity.

Secondary Objective:

1. To assess the safety and tolerability of perampanel as an adjunctive AED in patients with primary glioma presenting with refractory partial onset seizure activity.

Exploratory Objective:

1. To evaluate the effect that perampanel has on neurocognition and patient-reported outcomes of quality of life (QoL) in patients with primary glioma presenting with refractory partial onset seizure activity.

Hypothesis:

We hypothesize that the addition of perampanel as an adjunctive AED will be effective in treating patients with primary glioma that are presenting with refractory partial onset seizure activity on non-enzyme inducing anti-epileptic drug regimen.

3.2 Design and Procedure

This is a Phase 4 single-arm study to assess the efficacy of perampanel as an adjunct anti-epileptic in patients with primary glioma that are presenting refractory partial onset seizure activity (defined as 3 or more seizures in a 28-day period). In this study, patients will be started on a dose of 2 mg of perampanel daily taken orally at bedtime for 2 weeks. At the start of week 3 Perampanel will be titrated up in dose in 2mg increments per week up to 8mg daily, as long as it is well tolerated by the patient. The highest dose of perampanel will be 8 mg orally at bedtime. Patients will begin the treatment period of the study starting at week 5 and will continue through the end of week 12. The planned treatment dose is 8mg, but the dose can be modified by the physician based on patient reported tolerability. Patients will be assessed in the Brain Tumor Center Clinic every 8 weeks. Study assessments will be made at enrollment, 8 weeks, 16 weeks, and 24 weeks.

Assessments will include history and physical examination (H&P) including Karnofsky Performance Status (KPS), neurological examination, evaluation of seizure history, patient-reported outcomes of QoL, and neurocognitive testing using CNS Vital Signs®. After a total of 16 weeks of therapy, perampanel will be tapered for 3 weeks and then will be discontinued, such that at week 20, patients will only be taking their original AED regimen. Patients will then be monitored through Week 24. Patients will remain on their original AED therapy during this treatment time and the dose of their original AED regimen at the start of the study will not be changed while they are on study. If seizure control is achieved during the treatment period or if seizures occur during the tapering period, patients can be continued on perampanel per the discretion of the treating physician. In this instance, perampanel will be prescribed by the treating physician and not provided within the confines of the study. Efficacy will be assessed using a log of patient-reported seizure activity. As is standard procedure at the PRTBTC, patients will be given a log to record the number of seizures that occur. Research team members will regularly contact patients for reminders and reports from the log. Safety will be assessed with the following laboratory evaluations: complete blood count (CBC) with differential, complete metabolic panel (CMP), and toxicity assessment.

3.3 Selection of Subjects

Inclusion Criteria:

1. Patients must be diagnosed with a primary glioma and have refractory partial onset seizure activity (defined as 3 or more seizures in a 28-day period) on non-enzyme inducing anti-epileptic regimen that can

include, but not limited to the following: levetiracetam (Keppra) or Keppra XR, lamotrigine (Lamictal) or Lamictal XR, gabapentin (Neurontin), tiagabine (Gabitril), topiramate (Topamax), valproic acid (Depakene) / valproate (Depacon), zonisamide (Zonegran), lacosamide (Vimpat), and clonazepam (Klonopin)

2. Adult patients (\geq 18 years old)
3. Karnofsky \geq 70%
4. Hematocrit \geq 29%, ANC \geq 1,500 cells/L, platelets \geq 100,000 cells/L
5. Serum creatinine \leq 1.5 mg/dL, serum AST and bilirubin \leq 1.5 times the upper limit of normal
6. If sexually active, patients will take contraceptive measures for the duration of protocol treatment and continue until two months after treatment. The effectiveness of hormonal contraceptives containing levonorgestrel has been shown to be reduced by perampanel at a 12 mg dose.¹ Therefore, alternative or back-up methods of contraception are recommended.
7. Signed informed consent approved by the Duke Institutional Review Board

Exclusion Criteria:

1. Pregnant or breastfeeding (Both perampanel and levetiracetam are classified as Pregnancy Category C drugs.)
2. Chronic excessive use of psycho-pharmaceuticals, alcohol, illicit drugs, or narcotics
3. Inability to complete or perform measures of patient-reported outcomes or neurocognitive testing on the computer
4. Known allergy to perampanel
5. Concomitant use of known cytochrome P450 (3A4,5,7) inducers such as carbamazepine, phenytoin, or oxcarbazepine (see Appendix A)
6. Previous history of suicidal ideation, homicidal ideation, depression leading to hospitalization or mood disturbance leading to hospitalization.

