7 INVESTIGATIONAL PLAN

7.1 Study Design

This is a Phase 4 single-arm study assessing the efficacy of perampanel as an adjunct anti-epileptic drug (AED) in patients with primary glioma presenting refractory partial onset seizure activity (defined as 3 or more seizures in a 28-day period). All primary glioma patients that have refractory partial onset seizures can be considered for this clinical trial if they meet the eligibility criteria. This will include patients that are receiving active chemotherapy, which could include, but is not limited to, the following agents: temozolamide, bevacizumab, irinotecan, etoposide, lomustine, carboplatin. All concomitant medications will be recorded during the study. The study will enroll approximately 71 patients at the PRTBTC at Duke.

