Perampanel will be given according to FDA-approved guidelines over a 24-week period. Patients will be started on a dose of 2 mg daily taken orally at bedtime for 2 weeks. At the start of week 3 Perampanel will be titrated up in dose in 2mg increments per week up to 8mg daily, as long as it is well tolerated by the patient. Weeks 1 and 2, patients will take 2mg, Week 3 they will take 4 mg, Week 4 they will take 6mg and starting at week 5 they will take 8mg. Highest dose will be 8 mg orally at bedtime. Starting at week 5, patients will begin the treatment period, which goes from day 1 of Week 5 through day 7 of Week 16. Patients will be assessed in the Brain Tumor Center Clinic every 8 weeks. Assessments will be made at enrollment, 8 weeks, 16 weeks, and 24 weeks. Assessments will include history, physical examination, neurological examination, evaluation of seizure history, patient-reported outcomes of quality of life, and neurocognitive testing using CNS Vital Signs®. After a total of 16 weeks on therapy, perampanel will be tapered down. At Week 17, patients will begin taking 6mg of perampanel, Week 18 4mg, Week 19 2mg, and Week 20 they will no longer take perampanel. Patients will be considered off treatment at the end of week 20, once perampanel has cleared their system. The planned treatment dose is 8mg, but the dose can be modified by the physician based on patient reported tolerability. Titration and taper periods will be determined by the physician in the case where patients do not reach the planned treatment dose of 8 mg daily. Patients will continue to take their original AED regimen after they stop perampanel. Patients will then be monitored through Week 24. Patients will remain on their original AED regimen during this treatment time and the dose of their original AED at the start of the study will not be changed while they are on study. If seizure control is achieved during the treatment period or if seizures occur during the tapering period, patients can be continued on perampanel per the discretion of the treating physician. In this instance, perampanel will be prescribed by the treating physician and not provided within the confines of the study. As is standard procedure at the PRTBTC, patients will be given a log to record the number of seizures that occur. Research team members will regularly contact patients for reminders and reports from the log.

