10 SCREENING AND ON-STUDY TESTS AND PROCEDURES

Table 1: Study Assessment Schema

	Baseline within 4 weeks of initiation of study drug	8 weeks after initiation of study drug	16 weeks after initiation of study drug	24 weeks after initiation of study drug
CBC with diff	X	X	X	X
CMP	X	X	X	X
H&P, including KPS and concomitant medications	X	X	X	X
Complete Neurological Examination	X	X	X	X
Toxicity assessment using CTCAE v.4 guidelines			Ongoing ²	
Urine pregnancy test ¹	X			
Seizure History/Log	X ³		Ongoing ⁴	
QoL Questionnaires	X	X	X	X
Neurocognitive Testing	X	X	X	X

¹ For women of childbearing potential, within 48 hours prior to initiation of study drug, if contraception not initiated at time of negative test result prior to that time. Urine pregnancy test will be conducted according to Duke IRB and DOCR guidelines.

² Toxicities will be recorded from the time the subject starts study drug.

³ Number of seizures in past 28 days

⁴ Subjects will be given a seizure log to record the number of seizures that occur, as is standard procedure at the PRTBTC.

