10.1 Screening Examination

The screening examination will take place within 4 weeks of initiation of study drug. An informed consent must be signed by the patient before any screening procedures take place. Subject data to be collected at the Screening Examination includes the following:

Pre-treatment evaluations to determine eligibility will include the following:

- History and physical exam, including KPS and a full neurologic assessment
- Seizure history
- CBC with differential, CMP, Beta-HCG if appropriate (within 48 hours of beginning study drug, if contraception not initiated at time of negative test result prior to that time). Urine pregnancy test will be conducted according to Duke IRB and DOCR guidelines.
- Quality of life measurements and neurocognitive testing, as a baseline

If a subject is found to be ineligible to participate in the study, minimal records regarding the subject and the reason for screen failure will be retained in the study database.

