10.2 Run-In Period

Not applicable.

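### Nothing at entry requires an unchanged AED regimen over the 28-day baseline count or up to first dose, so in this single-arm trial the effect of a recent background change can be credited to perampanel

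*Combined protocol and SAP*

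**What the plan says.** **Entry.** Section 3.3, Inclusion Criterion 1, admits patients who "have refractory partial onset seizure activity (defined as 3 or more seizures in a 28-day period) on non-enzyme inducing anti-epileptic regimen". Refractory is defined by the count alone. None of the seven inclusion or six exclusion criteria sets a minimum time on an AED, a stable dose, or a bar on a recent change.

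**Baseline count.** Table 1 in Section 10, footnote 3, gives the baseline seizure measure as "Number of seizures in past 28 days". It is retrospective. Section 10.1 adds that "The screening examination will take place within 4 weeks of initiation of study drug". Section 10.2 answers the run-in heading with "Not applicable".

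**Dose freeze.** Section 7.1 says "the dose of their original AED at the start of the study will not be changed while they are on study", and Section 3.2 has the same rule. Neither defines the start of the study.

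**Analysis.** Section 13.4.1 compares seizure frequency in the treatment period with frequency before perampanel. Section 13.4.2 tests the 50% responder rate against 20% with a one-sample binomial test at the 0.1 level. Concomitant medications are recorded (Sections 7.1 and 10.8.1), but Section 13 does not use them to exclude, adjust for or examine recent AED changes.

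**The concern.** The primary objective is the effect of perampanel added to an existing regimen. A before-and-after comparison isolates that effect only if the existing regimen is the same on both sides.

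Consider a patient with four seizures in the past month while on an AED, whose dose of that AED was raised last week. This patient meets Inclusion Criterion 1. The baseline count comes mostly from the old dose, and Weeks 5 to 16 come from the new dose plus perampanel. A second AED added, or one AED switched for another, late in the window or after it has the same effect.

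This is not chance regression to the mean. It is a real treatment change inside the comparison. In a randomised trial such changes would be expected to balance between arms. Here there is no second arm, so any benefit from them goes into the responder count that is set against 20%.

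**Working it through.** **1. How far back the unprotected interval reaches.** The count covers 28 days (Table 1, footnote 3) and is taken up to 4 weeks, or 28 days, before first dose (Section 10.1). The earliest counted day can therefore lie about 28 + 28 = 56 days before perampanel. No entry criterion fixes the AED regimen at any point in that interval. The freeze covers its last part only if the start of the study means consent or enrolment and not first dose.

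**2. The plan's own figure.** The inputs are a null rate of 0.20, an alternative of 0.35, a type I error of 0.1, power of 90% and 61 patients (Sections 3.5 and 13.8). The plan does not say whether the test is one-sided. With X the number of responders among n, the exact one-sided rule rejects when X ≥ r, where r is the smallest value with P(X ≥ r | 0.20) ≤ 0.1.

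- n = 61: r = 17, P(X ≥ 17 | 0.20) = 0.088, P(X ≥ 17 | 0.35) = 0.905.
- n = 60: r = 17, power 0.890, which is below 90%.
- Two-sided 0.1 (upper tail 0.05) at n = 61: r = 18, power 0.850, which does not meet the plan.

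So 61 reproduces with a one-sided exact test, and the working rule is 17 or more responders of 61.

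**3. Effect of background changes.** Suppose perampanel adds nothing and stable patients respond at 20%. A share f of evaluable patients had a recent AED change and respond at rate q. The no-effect responder rate is then

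p = 0.20(1 − f) + q·f = 0.20 + f(q − 0.20),

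and the false-positive rate is P(X ≥ 17 | 61, p). The documents give neither f nor q, so both are assumptions.

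| Assumed f and q | p | Expected responders, 61p | False-positive rate |
|---|---|---|---|
| none changed | 0.200 | 12.2 | 0.088 |
| 5%, 30% | 0.205 | 12.5 | 0.105 |
| 5%, 40%; or 10%, 30% | 0.21 | 12.8 | 0.125 |
| 10%, 40%; or 20%, 30% | 0.22 | 13.4 | 0.170 |
| 20%, 40% | 0.24 | 14.6 | 0.283 |
| 30%, 40% | 0.26 | 15.9 | 0.417 |

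The nominal 0.10 is passed once p exceeds about 20.4%. At p = 0.22, an average of 61 × 0.02 = 1.2 extra responders, the false-positive rate is 0.170 / 0.088 = 1.9 times the rule's actual size.

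**The case against.** **The freeze.** The plan does control background AEDs: doses may not change on study. This stands for the treatment period, where it removes one source of bias. It does not reach back over the count. If a dose was raised just before the freeze began, the freeze keeps the new dose in place through Week 16 while the baseline still reflects the old one. If the start of the study means consent or enrolment, changes from then to first dose are already barred and only the retrospective count is exposed. The documents do not settle this.

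**Being on a regimen.** The criterion requires seizures on an AED regimen. On a plain reading, a patient whose first-ever AED began after the counted seizures does not qualify. That stands, and the point is limited to raised, added or switched AEDs.

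**Size and direction.** Nothing in the documents shows that any patient had a recent change. That uncontrolled seizures prompt AED increases is plausible but not stated, and a recent reduction would bias the other way. A change early in the 28-day window leaves most of the count on the new regimen, so only late changes contaminate it strongly. The 20% comes from standard-treatment arms of randomised studies whose AED stability rules are not given, so the benchmark may already contain some of this effect. All of this limits what can be said about magnitude. None of it closes the gap in the entry rule.

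**A stronger reading.** A reader might infer that the trial will credit AED changes to perampanel, or that its type I error is in fact 0.17 or more. The documents support only that this can happen, and the rates in the table depend on assumed inputs.

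**Conclusion.** The gap is real and lies in the text: eligibility does not tie the baseline count to an unchanged AED regimen, and the forward freeze does not make up for it. Following the plan as written can bias the primary result, most plausibly towards a positive finding. The textual point is firm, but the size is unknown. The illustrative false-positive rates (0.125, 0.170 and 0.283 at no-effect responder rates of 21%, 22% and 24%, against 0.088 at 20%) assume 61 evaluable patients, the one-sided exact rule, a true 20% response in stable patients, and chosen values for the share of changed patients and their response. They show that the test has little room for even a small shift. They do not estimate the shift. The change should be made because it protects the primary comparison at little cost; the sample size of 61 is unaffected.

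**What to change.** 1. **Entry.** Add to Inclusion Criterion 1 that the AED regimen, both drugs and doses, was unchanged over the same window that supplies the baseline seizure count and up to the first perampanel dose. Any stability period longer than that is for the sponsor to set.
2. **Freeze.** Define the start of the study for the dose freeze in Sections 3.2 and 7.1, so that no gap is left between the count and first dose.
3. **Data and analysis.** Record the date and nature of the last AED change at screening. Add to Section 13.4.2 a sensitivity analysis that reports the responder rate excluding patients with a change in that window. Apply it to patients already enrolled where their history gives dates. The protocol does not require change dates, so it should not be assumed that they are available for everyone.

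**Cost.** Accrual is slightly slower, because a patient with a recent change would need a new baseline window on the unchanged regimen and a few may then no longer qualify. One extra date is recorded. No new visit or test is needed.

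This is a condition for entering the analysis. It does not say how a patient's AEDs should be managed before entry.

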3.4 Risk/Benefit Assessment

The full prescribing information for Perampanel (FYCOMPA™) includes the following boxed warning¹:

WARNING: SERIOUS PSYCHIATRIC AND BEHAVIORAL REACTIONS

- Serious or life-threatening psychiatric and behavioral adverse reactions including aggression, hostility, irritability, anger, and homicidal ideation and threats have been reported in patients taking FYCOMPA
- These reactions occurred in patients with and without prior psychiatric history, prior aggressive behavior, or concomitant use of medications associated with hostility and aggression
- Advise patients and caregivers to contact a healthcare provider immediately if any of these reactions or changes in mood, behavior, or personality that are not typical for the patient are observed while taking FYCOMPA or after discontinuing FYCOMPA
- Closely monitor patients particularly during the titration period and at higher doses
- FYCOMPA should be reduced if these symptoms occur and should be discontinued immediately if symptoms are severe or are worsening

The most common adverse reactions that are associated with perampanel occurring in 10% of patients or greater are dizziness (36%), somnolence (16%), and fatigue (10%). Less common reactions are irritability (9%), falls (7%), nausea (7%), ataxia (5%), balance disorder (4%), gait disturbance (4%), vertigo (4%), and weight gain (4%).

With concomitant use, perampanel, at a dose of 12 mg/day, reduced levonorgestrel exposure by approximately 40%. Use of perampanel with oral or implant contraceptives containing levonorgestrel may render them less effective. Therefore, additional non-hormonal forms of contraception are recommended (please see the FYCOMPA FDA-approved labeling dated 6/11/2013).¹

The concomitant use of known CYP enzyme inducers including carbamazepine, phenytoin, or oxcarbazepine with perampanel decreased the plasma levels of perampanel by approximately 50~67%. The starting doses for perampanel should be increased in the presence of enzyme-inducing AEDs.¹ When these enzyme-inducing

AEDs are introduced or withdrawn from a patient's treatment regimen, patient should be closely monitored for clinical response and tolerability. Dose adjustment of perampanel may be necessary. As noted, however, the decrease in the therapeutic effect seen in patients on concomitant treatment, was not affected by use of higher doses (8 mg to 12 mg).¹

Concomitant use of perampanel with other strong CYP3A inducers (e.g., rifampin, St. John's wort) should be avoided.¹

The concomitant use of perampanel and CNS depressants including alcohol may increase CNS depression.¹ A pharmacodynamic interaction study in healthy subjects found that the effects of perampanel on complex tasks such as driving ability were additive or supra-additive to the impairment effects of alcohol. Multiple dosing of perampanel 12 mg/day also enhanced the effects of alcohol to interfere with vigilance and alertness, and increased levels of anger, confusion, and depression. These effects may also be seen when perampanel is used in combination with other CNS depressants. Care should be taken when administering perampanel with these agents. Patients should limit activity until they have experience with concomitant use of CNS depressants (e.g. benzodiazepines, narcotics, barbiturates, sedating antihistamines). Advise patients not to drive or operate machinery until they have gained sufficient experience on perampanel to gauge whether it adversely affects these activities.¹

[figure not shown]
3.5 Data Analysis and Statistical Considerations

The one-arm study will assess the efficacy of perampanel for the treatment of primary brain tumor patients with partial onset seizures. The basis for this assessment is the percentage of patients with a $\geq 50\%$ seizure reduction during the treatment period compared with seizure frequency before initiation of perampanel (i.e. 50% responder rate).

Several recent conducted randomized studies of patients with partial-onset seizures have reported a 50% responder rate of approximately 20% within the standard treatment arm.²⁻⁴ Steinhoff (2009) also reports a 50% responder rate of approximately 35% within a general population of patients with partial-onset seizures treated with perampanel.⁵

This study has been designed with 90% power to detect an increase in the 50% responder rate during the treatment period from a benchmark of 20% to 35%. Assuming a type I error rate of 0.1, 61 patients will be required. Based on prior studies the early discontinuation rate was 16%, therefore 71 patients will be enrolled to compensate for patients discontinuing prior to the completion of the treatment period.

